8.4.2. Follow-up of withdrawn subjects, drop outs

A drop out is a subject, who prematurely discontinues participation after being enrolled. If a subject drops out, possible AE's will be recorded as long as necessary. A post-study examination should be performed if possible.

All AE's documented during the study for the drop out will be considered in the assessment. Other data recorded for the drop out are contained in the individual subject listing in an appendix to the study report.

8.4.3. Premature Termination of the study

The sponsor has the right to close this study, and the Principal Investigator has the right to close the centre, at any time, although this can occur only after consultation between involved parties. The Independent Ethics Committee (IEC) and the Institutional Review Board (IRB) must be informed. If the study/centre had to be closed prematurely, the study centre will provide all essential documents necessary for the sponsor's trial master file (TMF), as defined in the GCP Note for Guidance.

The trial will be terminated prematurely in the following cases:

- If AE's occur which are so serious that the risk-benefit ratio is not acceptable.
- If the trial conduct (e.g. recruitment rate, drop-out rate, data quality, protocol compliance) does not suggest a proper completion of the trial within a reasonable time frame.

8.4.4. Replacements

Subjects who prematurely discontinue participation will not be replaced.

8.4.5. Removal of volunteers from assessment Screening failures

Screening failures are volunteers who were screened but not enrolled. Screening failures including reason will be listed in the screening list. All data obtained within the screening will be documented in the subject's record. In case that entries were made to a CRF it will be archived, but not entered in the database. Screening failures will not be listed, as no CRF data is included in the database.

8.5. Intention-to-treat (ITT) and Safety population

The safety set/population consists of all subjects who were randomised and exposed to study medication.

The ITT population contains any subject included and randomized in the study, with available baseline value of the primary endpoint and at least one follow-up visit for the efficacy parameters.

8.6. Eligibility Criteria

8.6.1. Inclusion Criteria

Deviations from inclusion criteria are not allowed because they can potentially jeopardize the scientific integrity of the study, regulatory acceptability or subject safety. Therefore, adherence to the criteria as specified in the protocol is essential.

A subject will be eligible for inclusion in this study only if all the following criteria apply:

1. Gender: male / female.
2. Women of childbearing potential is a premenopausal female that is anatomically and physiologically capable of becoming pregnant following menarche.

Female subjects: are women of childbearing potential who test negative for pregnancy and agree to use a reliable method of birth control or remain abstinent during the study. Methods of contraception

considered acceptable include oral contraceptives, contraceptive patch, intrauterine device, vaginal ring, diaphragm with contraceptive gel, or condom with contraceptive gel

-or

are women of non-childbearing potential, defined as: women who have had surgical sterilization (hysterectomy, bilateral oophorectomy, or tubal ligation),

-or women who are ≥60 years of age.

3. Age: ≥ 2 year of age at the time of enrollment.
4. Subject must have an active head lice infestation defined as at least 5 live lice (adults and/or nymphs) and 5 apparently live nits, present on the scalp and/or hair, as determined by a trained evaluator.
5. Subject is in good general health based on medical history.
6. The subject or his/her parent/legal guardian must give written informed consent, after having been oral and written informed about benefits and potential risks of the trial, as well as information regarding the insurance, taken out to cover the subjects participating in the study. A caregiver must sign an informed consent agreement for children not old enough to do so. Children ages 6-18 years of age will be administered a child's assent form. Subject or his/her parent/legal guardian must be capable of understanding and providing written informed consent.
7. Following application and rinsing of the test products, subject agrees not to shampoo, wash, or rinse their hair or scalp until the 24-hour post treatment evaluation has been completed.
8. The subject agrees not to cut or chemically treat their hair while participating in the study.
9. No more than one working male per household may be excluded from evaluation if he is assessed as being lice free by himself or caregiver.
10. Subject agrees to follow all study instructions, including attending all follow-up appointments.
11. Agree to not use any other pediculicides or medicated hair grooming products for the duration of the study (through Day 10 visit).
12. The parent or legal guardian of a child must be willing to have other family members screened for head lice. If other household members are found to have head lice and are eligible, they must be either enrolled in the study OR receive the standard of care at the site and in the same manner as study participants.
13. Have a single place of residence.
14. The subject or his/her parent or legal guardian must give written informed consent, after having been oral and written informed about benefits and potential risks of the trial, as well as details of the insurance taken out to cover the subjects participating in the study
15. Subjects must agree to not use any other ant-lice treatment for the duration of the study

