2. INTRODUCTION

Head lice (*Pediculus humanus capitis*) are parasitic insects that can be found on the head, of humans, particularly school age children. Head lice are tiny, wingless insects (2-3 mm in length) which live among the warmth of human hair, usually close to the scalp, and feed from the blood in the scalp. They crawl but cannot fly or hop. Although small, head lice can be seen with the naked eye. However, a magnifying glass may facilitate observation. When head lice bite the scalp to feed on the blood, it may cause itching; when lice crawl, it can cause a tickling/itching sensation. Lice are also more active in the dark, disrupting the infested person's sleep.

Female lice lay 3-5 eggs (also called nits) per day, which take 1-2 weeks to hatch. Nymphs need 7-10 days to become adult lice. Head lice infest the head and neck and the nits attach to the base on the hair shaft, generally within $\frac{1}{4}$ inch of the scalp. Head lice survive on the human host for up to 30 days.

Lice are spread by direct contact with an infested individual or contact with clothing, worn by the infested individual, or with personal items (e.g., hair brushes, hair ties, towels, bed linens, etc.). Personal hygiene or cleanliness has nothing to do with getting lice. There is no evidence that lice prefer clean or dirty hair or whether the length of the hair increases the risk for being infested with lice. Head lice do not carry diseases, nor can they survive on non-humans (e.g. pets do not transmit). When removed from the human host, head lice usually die within 24 hours. Also, when lice are in water, they become extremely inactive but remain firmly attached to the hair. For this reason, lice are generally not transmitted in the swimming pool; however, sharing the towel, used to dry the hair of the infested individual, may contribute to transmitting head lice.

Head lice are very common; about 10% of the population are infested. From 6 to 12 million infestations occur in the United States each year in children aged 3 to 12 years of age. It occurs more frequently in girls than boys. It occurs less frequently in African Americans than other races; this might be explained by the shape and thickness of the hair shaft.

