12.3. Volunteer information and consent

12.3.1. Informed consent and assent

The subject will receive a consent form. The subject information document contains all relevant information about the study in accordance with the GCP requirements. Every subject must be informed verbally and in writing by receiving the subject information document. The written information for subjects must be approved by Ethics Committee. The consent form must be signed and dated by the

subject prior to the start of the study. The informed consent form must be signed and dated by the physician who conducted the informed consent discussion. The subjects must be given a copy of the document.

The Principal Investigator must ensure that subjects are clearly and fully informed about the purpose, potential risks and other critical issues regarding clinical studies in which they volunteer to participate. The principles of Informed Consent, according to FDA Regulations and ICH GCP, will be followed. A copy of the proposed consent form must be submitted to the IRB, together with the protocol, for approval. Prior to beginning of the study, the Principal Investigator must have the IRB's written approval of the written informed consent form, assent form, and any other information to be provided to Subjects.

Every subject has the right to refuse further participation in the study at any time and without giving reasons. Confidentiality and pseudonymity of the subjects are assured. Children from 2-11 years and adolescents from 12 to less than 18 years can be included in this study. However, special requirements for this subject group are described below.

As the minor is unable to provide legally binding consent, the parent/s or legal guardian has/have to give informed consent on his/her behalf prior to enrolling a minor in the trial. In case both parents are the legal guardian, it may be sufficient that at least one parent gives the informed consent.

The parent(s)/legal guardian will be given sufficient time and necessary information to consider the benefits and risks of involving the minor in the clinical trial. Information will be given by experienced personnel to parent(s), or the legal guardian on the purpose of the trial and its nature, the potential benefits and risks, and the name of investigator(s) who are responsible for conducting the trial with background professional information (such as education, work experience) and direct contact details (telephone, address, e-mail).

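### Inclusion criterion 2 gives girls before menarche and unsterilised postmenopausal women under 60 no eligible category, contradicting the protocol's stated population

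*Combined protocol and SAP*

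**What the plan says.** Section 8.6.1 sets a strict frame for eligibility: "A subject will be eligible for inclusion in this study only if all the following criteria apply". It adds: "Deviations from inclusion criteria are not allowed because they can potentially jeopardize the scientific integrity of the study". Section 8.2 then reserves randomisation for those who meet the inclusion criteria.

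Within that frame, criterion 2 starts from a definition: "Women of childbearing potential is a premenopausal female that is anatomically and physiologically capable of becoming pregnant following menarche". It goes on to list who may enter:

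- Category 1: "Female subjects: are women of childbearing potential who test negative for pregnancy and agree to use a reliable method of birth control", or remain abstinent.
- Category 2: females who "are women of non-childbearing potential, defined as: women who have had surgical sterilization", with three operations named, or who are at least 60 years old.

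Other parts of the protocol describe a wider population. Criterion 3 sets the lower age limit at 2 years. Sections 3 and 6.1 refer to both sexes from that age. Section 12.3.1 states: "Children from 2-11 years and adolescents from 12 to less than 18 years can be included in this study". Section 2 places US infestations in children aged 3 to 12 and says of the condition: "It occurs more frequently in girls than boys".

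**The concern.** Criterion 2 reads as a complete list of the females who may be enrolled, but the list has a gap at each end of reproductive life. Its first category begins at menarche and stops at menopause. Its second covers only surgical sterilisation and age 60 or over. Anyone between these limits has no route into the trial if the text is followed.

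A site that applies the criterion literally turns away young girls whom the rest of the protocol plainly means to enrol, and the results then generalise to a narrower group. A site that follows the evident intent enrols them against a criterion the protocol calls essential. Section 6.1 describes two centres, so both readings could operate at once and produce different populations by centre.

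**Working it through.** The protocol gives no figure to reproduce on this point. The check treats criterion 2 as a rule and applies it to female profiles.

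**The rule, from Section 8.6.1**

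- C (childbearing potential): premenopausal, past menarche and able to become pregnant. The text is "premenopausal female that is anatomically and physiologically capable of becoming pregnant following menarche".
- N (non-childbearing potential): surgically sterilised, or aged 60 or over.
- A female meets criterion 2 if she is in C (with a negative test and contraception or abstinence) or in N.

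**Applied to profiles**

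| Female profile | In C? | In N? | Result |
|---|---|---|---|
| Age 2, before menarche | No | No | Neither |
| Age 8, before menarche | No | No | Neither |
| Age 11, before menarche | No | No | Neither |
| Age 14, after menarche, not sterilised | Yes | No | Category 1 |
| Age 35, premenopausal, not sterilised | Yes | No | Category 1 |
| Age 40, sterilised | No | Yes | Category 2 |
| Age 55, postmenopausal, not sterilised | No | No | Neither |
| Age 60, postmenopausal, not sterilised | No | Yes | Category 2 |

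**Set against the rest of the protocol**

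- The girls aged 2, 8 and 11 satisfy criterion 3 and fall in the child age band of Section 12.3.1, but fail criterion 2. Because all criteria must hold, they are ineligible as the text stands.
- The woman of 55 satisfies criterion 3, and Section 6.1 gives no upper age limit. She also fails criterion 2.
- Sections 6.2, 6.7 and 9.4.6 confine the pregnancy test to females of childbearing potential. That implies other females were expected, but it creates no eligibility category for them.
- Section 6.6 points the other way. It addresses its contraception instruction to female subjects in general, with no exception for girls before menarche.

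**Number affected.** The count would be 70 × s, where 70 is the planned enrolment (Section 8.1) and s is the share of subjects in the uncovered groups. The documents do not give s and offer nothing to bound it. Enrolment also takes in boys, adults of any age and infested household members. No count can be derived.

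**Effect on the analysis.** Sections 8.5 and 10.4 define the ITT set by inclusion, randomisation, a baseline value and at least one follow-up visit. The safety set in Section 8.5 needs only randomisation and exposure. Neither definition tests eligibility, and no per-protocol set is defined.

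**The case against.** The strongest reply is that nobody would read criterion 2 as barring girls. The list cannot be a literal conjunction for every subject: criterion 2 says nothing about males, criterion 12 concerns parents and guardians, and criterion 9 is not a subject-level condition. A reader already applies each item only to those it addresses. Criterion 2 deals with pregnancy and speaks of women, and the data table in Section 9.8 marks the childbearing fields as applying to women only. Sections 3, 6.1 and 12.3.1 make the intent to enrol children of both sexes clear, and Sections 12.3.2 and 12.3.3 set consent rules for pre-school and school-age children.

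Much of this stands. It shows a drafting omission rather than a deliberate restriction, and it makes it likely that sites would enrol girls. It does not close the gap. The two categories are introduced under female subjects, the definition speaks of a female and uses menarche as its threshold, and no text exempts girls before menarche. Evident intent elsewhere confirms that rule and purpose diverge. The postmenopausal gap is untouched by the argument about the word women.

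Three stronger readings are tempting, but the documents do not support them:

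- A reader might infer that the trial could not answer its question. The primary objective in Section 5.1 concerns a cure rate in infested subjects. Boys, men and females in either category remain eligible under the literal rule, so the loss is one of generalisability.
- A reader might infer that ineligible subjects would later be dropped from the analysis. Neither analysis set has an eligibility condition. Section 8.4.1 does list relevant procedural deviations as a ground for withdrawal, but it provides no analysis exclusion for failing an entry criterion.
- A reader might take girls before menarche to be the group Section 2 calls most affected. Section 2 gives an age range and, separately, a sex difference. It neither mentions menarche nor ranks that subgroup.

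**Conclusion.** The criterion is wrong as written, with low severity. Followed exactly, it bars girls before menarche and unsterilised postmenopausal women under 60. That contradicts criterion 3 and Sections 3 and 6.1, and for the girls also Section 12.3.1. The consequences fall on eligibility, recruitment, consistency between the two centres and generalisability. The primary estimate is not directly biased, provided the ITT definition in Sections 8.5 and 10.4 is respected.

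The conclusion rests on the wording of Section 8.6.1 alone and needs no assumption about numbers. A reader might suppose that a large, specific share of the 70 subjects is affected. The documents give no basis for any such figure.

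**What to change.** Before enrolment, reconcile criterion 2 with criterion 3 and Sections 3, 6.1 and 12.3.1, so that every female the protocol intends to enrol falls in an eligible category. The revised text should state how girls before menarche and postmenopausal women under 60 are classed.

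In the same revision, reconcile to whom the contraception and pregnancy-test wording applies across Sections 6.2, 6.6, 6.7, 8.6.1 and 9.4.6. Editing criterion 2 alone would leave the general instruction in Section 6.6 in conflict. The clinical content of those conditions is for the sponsor and investigator to settle; the point here is that the sections must agree.

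The cost is a wording change to the protocol and the matching CRF fields. Design, sample size and analysis are unaffected.

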8.6.2. Exclusion Criteria

Deviations from exclusion criteria are not allowed because they can potentially jeopardize the scientific integrity of the study, regulatory acceptability or subject safety. Therefore, adherence to the criteria as specified in the protocol is essential.

A subject will not be eligible for inclusion in this study if any of the following criteria apply:

1. Application of any form of head lice treatment, whether prescription or over-the-counter (OTC), or home remedy for 30 days prior to their screening visit (Day 1).
2. Application of any topical medication of any kind on the hair for a period of 48 hours prior to the screening visit.
3. Use of systemic or topical drugs or medications, including systemic antibiotics, which in the opinion of the investigative personnel may interfere with the study results.
4. Known skin allergies, multiple drug allergies or multiple allergies to cosmetic products.
5. History of allergy or hypersensitivity to ragweed, active ingredients or constituents of the test products.
6. Subject with any visible skin/scalp condition at the treatment site which, in the opinion of the investigative personnel, will interfere with the evaluation of the test product.
7. Subjects with chronic scalp disorder.
8. Subject or his/her legal guardian who, in the opinion of the investigative personnel, do not understand the subject requirements for study participations and/or may be likely to exhibit poor compliance with the required visits.
9. Females who are pregnant or nursing.
10. Hair longer than mid-back.
11. Subject suspected or known not to follow instructions
12. Previous participation in this study or participation in any other investigational trial within the preceding 30 days
13. The subject is directly affiliated to the investigator site personnel and/or their immediate families. Immediate family is defined as a spouse, parent, child, or sibling, whether biological or legally adopted
14. The subject is an Oystershell employee or is an employee of a third-party organizations involved in the study.

9. STUDY ASSESSMENTS AND PROCEDURES

This section lists the parameters of each planned study assessment. The exact timing of each assessment is listed in the Time and Events Table (Section 6.7).

Assessments for skin irritation and eyes irritation prior to administration (baseline as well as assessments on day 7) will be performed within 1 hour before administration.

Assessments for local tolerability, global tolerability (V4), skin irritation and eyes irritation after administration will be performed directly after start of the treatment plus 5 minutes as well as after the end of treatment (the contact time is over and the investigational product is rinsed) within 15 minutes. For all other assessments, a deviation up to \pm 20 min from scheduled time will be accepted.

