6.7. Time and Events Table

The actual date and time should be recorded for all procedures and the Investigator should make every effort to perform procedures as required by the protocol.

VISIT NUMBER	Visit 1			Visit 2	Visit 3	Visit 4
VISIT DAY	Day 0			Day 1 ± 3 hrs.	Day 7 + 1d	Day 10 +2d
VISIT NAME	Screening visit (baseline)			Evaluation Visit	Second treatment	Final Evaluation
	-1H	0	+1H			
Informed Consent	X					
Demographics (ethnic group, gender, age, hair length, height...)	X					
Medical history and medication usage	X					
Concomitant medication usage during study				X	X	X
Vital signs (blood pressure, pulse, respiratory and temperature)	X			X	X	X
Urine pregnancy test – child bearing potential	X					X
Physical examination of the scalp to verify head lice infestation by study staff	X					
Inclusion/exclusion	X					
Randomization study product		X				
Skin irritation – baseline assessment prior to treatment by blinded study staff	X				X	
Ocular irritation – baseline assessment prior to treatment by blinded study staff	X				X	
Application of study medication by unblinded study staff		X			X	
Global tolerability assessment by blinded study staff and subject						X
Local tolerability assessment (subjective symptoms: burning, paraesthesia, pruritus)	X		X	X	X	X
Skin and scalp irritation –by blinded study staff		X	X	X	X	X
Ocular irritation – post treatment assessment by blinded study staff		X	X	X	X	X
Adverse Events – questioning by blinded staff			X	X	X	X
Check of restrictions				X	X	X
Questioning on satisfaction with the esthetical effect			X		X	
Discharge from study						X

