8.3. Blinding

As both products are substantially different from each other in terms of packaging, smell and application method, it is not possible to do a double-blinded trial. Both, the subjects and the clinic personnel that will apply the investigational products, will be able to recognize the products. Therefore, an investigator-blinded study will be performed, and an independent assessor (investigator or study staff performing the assessments of hair and scalp, eyes, as well the efficacy and safety evaluations) will be blinded to the treatment. Appropriate measures will be taken to keep the assessor blind during the whole study. The assessor will not be involved in any procedure of the trial involving the handling, storage, and use of the products.

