9.4.4. Eye irritation assessment

To investigate a potential irritation of the eyes due to the treatment, the trained and blinded study staff will be assessed the severity of redness on both eyes (left, right) within 1 hours before first treatment (baseline), as well as directly after study drug application and after the end of treatment on study day 0, day 1, day 7 (pre-treatment, 0h and 1h p.a.) and on day 10. For the assessment of eyes, the following 4-category scale as mentioned above will be used.

- Score 1 = no
- Score 2 = mild
- Score 3 = moderate
- Score 4 = severe

It will be investigated, whether the investigational products may irritate the eyes.

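### As written, the assessor blind cannot be relied on for the Day 10 cure rate: blinded staff rate skin and eyes while the product is on the head, and nothing bars them from the lice counts

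*Combined protocol and SAP*

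**What the plan says.** Section 8.3 explains why a double-blind trial is not possible: "As both products are substantially different from each other in terms of packaging, smell and application method". Subjects and the personnel applying the product are expected to recognise it. The blind therefore rests on one role: "an independent assessor (investigator or study staff performing the assessments of hair and scalp, eyes, as well the efficacy and safety evaluations) will be blinded".

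Two safeguards follow in 8.3. The first is general: "Appropriate measures will be taken to keep the assessor blind during the whole study". The second is concrete: "The assessor will not be involved in any procedure of the trial involving the handling, storage, and use of the products".

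Section 9 sets two post-application readings of skin and eyes. Assessments for "skin irritation and eyes irritation after administration will be performed directly after start of the treatment plus 5 minutes"; the second reading comes only once contact time is over and the product has been rinsed out.

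Section 9.4.4 has trained, blinded staff rate eye redness "directly after study drug application and after the end of treatment on study day 0", and lists a 0h reading on Day 7 as well. Section 9.4.3 does the same for skin irritation. In the Time and Events Table (6.7), the Day 0 column at time 0 is marked for both ratings. The ocular row is labelled as a "post treatment assessment by blinded study staff", and the skin row also names blinded staff. The same table gives application of the product to unblinded staff.

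**The concern.** Subjects and applicators know the product, so the assessor is the only masked party. The primary endpoint depends on that assessor: cure means that a manual combing finds no living lice, corrected for re-infestation by a rule that uses the number and life stage of lice found (9.5). Both the search and the staging involve judgement.

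If the person making those calls has already stood over the treated head while the product was on it, the masking promised in 8.3 may have gone before the first efficacy count. The Day 0 reading precedes the counts on Days 1, 7 and 10. The Day 7 reading comes three days before the nominal Day 10 assessment. Knowledge of the product could then affect how persistently lice are sought, or how a doubtful nymph is staged.

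**Working it through.** The point is a conflict between sections. No figure in the plan has to be reproduced for it; the sample-size calculation does not enter.

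**1. Is the product on the head at the first reading?** Inputs: reading time from Section 9; contact times from 7.2, 7.5.1 and 7.5.2.

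| | Test product | Reference product |
|---|---|---|
| First reading, minutes after start of treatment | 0 to 5 | 0 to 5 |
| Earliest rinse, minutes | 15 | 10 |
| Earliest rinse minus latest reading | 15 − 5 = 10 | 10 − 5 = 5 |

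The reading precedes the rinse by at least 10 minutes in one arm and 5 in the other. This holds whether the 5 minutes is a time point or a tolerance. Counting contact time from the end of application, or using the permitted extra 2 minutes, only widens the gap. Section 7.5.1 adds that the hair is left uncovered in the test arm.

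**2. Who makes the reading?** Blinded staff, according to 6.7, 9.4.3 and 9.4.4. Section 8.3 agrees, since its blinded role includes eye and safety evaluations.

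**3. Could that person tell the products apart?** Section 8.3 names packaging, smell and application method. A rater who arrives after application need not see the packaging or the application. Smell remains, and 7.2 describes different forms (a two-phase lotion and a shampoo).

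**4. Does a safeguard prevent this?** The concrete one bars handling, storage and use. It does not bar examining, seeing or smelling a treated head. The general one names no measure.

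**5. Is the lice count kept separate?** Section 8.3 puts hair and scalp, efficacy, eyes and safety in one role. Section 6.4 gives the Day 7 lice examination to blinded staff. No section says that the irritation rater and the lice counter for a subject must be different people.

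**6. Which calls are exposed?** Under 9.5, re-infestation requires no adult lice or third-stage nymphs after the first treatment and no more than two on Day 10. The earlier counts and stagings therefore matter as well as the final one.

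**7. Scale.** With 35 subjects per arm (8.1), one subject is 1/35 = 2.9 percentage points. With the 30 per arm of 10.1 and 10.2, it is 1/30 = 3.3 points.

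The documents give no rate of assessor error. As an assumption only, take an exact one-sided 5% test of the test arm against 70% with n = 35. This is not the test named in 10.4.1. Success then needs 30 of 35 cures, with a type I error of 2.7%. Suppose the true cure rate is p = 0.70 and the assessor misses live lice in a fraction m of true failures. The observed rate is p + (1 − p)m:

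- m = 0.10: 0.73, probability of false success 6.0%
- m = 0.20: 0.76, probability 12.2%
- m = 0.30: 0.79, probability 22.7%

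These figures show sensitivity at the threshold. They do not estimate what would happen in this trial.

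**The case against.** A reader might infer that the blind is broken on Day 0. The documents do not go that far. Section 8.3 defines a role, the investigator or study staff, and not one individual. A site could use one rater for irritation and another for lice and so keep its promise. This stands. What remains is that the plan neither requires nor describes such a split.

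Recognition by the rater is also partly inferred. Section 8.3 states it for subjects and applicators, does not list appearance on the hair as a difference, and much of the test product's description is redacted. This also stands: smell is the supported route, and a claim resting on appearance would go too far.

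A reader might say that a single louse turns cure into failure. Under 9.5, up to two adult lice or third-stage nymphs on Day 10 can be classed as re-infestation. The search is also standardised in 9.4.8: three sections, six strokes each, with counts and life stages recorded. That limits discretion without removing it.

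Finally, a reader might put a size on the bias. If calls changed in opposite directions for one to three subjects per arm, the difference would move by 2/35 = 5.7 to 6/35 = 17.1 points, which looks alarming beside the 15-point superiority margin. The documents do not support this:

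- The number of changed calls is invented.
- At the planned 95% cure rate, the test arm expects only 0.05 × 35 = 1.75 failures, so three failures turned into cures is more than are expected.
- The between-arm difference is the secondary endpoint in 5.3.
- The planned difference is 95% − 55% = 40 points, well above the margin.

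**Conclusion.** The point holds as an internal contradiction that leaves the primary endpoint without reliable masking. Sections 6.7, 9, 9.4.3 and 9.4.4 send blinded staff to a head with the product still on it, on Day 0 and again on Day 7. Section 8.3 relies on staff in the same role being blind for the lice counts, and does not say how. The timing step is certain from the text.

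Two steps are inferences: that a rater at the head can recognise the product, chiefly by smell, and that the same person may go on to count that subject's lice. The plan permits the second; it does not prescribe it. The conclusion is therefore that the blind cannot be relied on as written, not that it has failed or that the result will be biased. The size of any bias cannot be derived from the documents; the only firm scale is 2.9 points of an arm's cure rate per subject at 35 per arm. The matter should be corrected because the remedy is cheap and protects the main outcome.

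**What to change.** Reconcile 6.7, 8.3, 9, 9.4.3 and 9.4.4 so that they state the following:

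- The 0h skin and eye readings made with the product on the head, on Day 0 and Day 7, are done by the unblinded staff already present for application.
- The lice-count assessor stays away from the subject until the hair has been rinsed and dried.
- Whoever made an on-head reading does not do that subject's lice counts at any visit.
- The CRF records a rater ID for each irritation reading and each lice count, so that the separation can be verified.

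In the same edit, align the timing of the second reading. Section 6.2 puts it 1 hour after the product is removed, while Section 9 refers to 15 minutes after the end of treatment. The blinded rater's earliest entry depends on which applies.

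The cost is protocol wording and one CRF field, using the two staff roles that the plan already has. The downside is that the 0h irritation ratings become openly unblinded and should be reported as such; the present text already compromises their masking. The later ratings stay with blinded staff. One route remains open: subjects know their product and are questioned about adverse events by blinded staff (6.7), so subjects should be asked not to name or describe it.
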